There has been no research on the value of cyanoacrylate embolization in the treatment of patients with chronic venous insufficiency and ulceration. Venous leg ulceration costs the NHS £600 million per year and affect 1.7% of the elderly population^{4,5}, making it a significant health problem that justifies further study.

We propose to define whether cyanoacrylate embolization is a safe and effective method of occluding incompetent lower limb veins in patients with venous ulceration of the lower limb.

PRIMARY OBJECTIVES

Our primary objectives are to answer the following research questions:

1. Does VenaSeal[™] cyanoacrylate occlusion of incompetent lower limb veins increase the rate of healing and shorten healing time in patients with an ipsilateral venous ulcer?

2. What is the incidence of venous recanalization following VenaSeal[™] cyanoacrylate occlusion for the treatment of ipsilateral venous leg ulcer?

3. Does VenaSeal[™] cyanoacrylate occlusion of incompetent lower limb veins improve quality of life and symptom severity scores in patients with venous leg ulcer?

4. What is the adverse effect profile of VenaSeal[™] cyanoacrylate occlusion of incompetent lower limb veins for the treatment of venous leg ulcers?

The overall aim of the research is to determine whether VenaSealTM cyanoacrylate occlusion of incompetent lower limb veins is an effective, safe and acceptable treatment in patients with ipsilateral venous leg ulcer.

STUDY DESIGN

This study is a randomised controlled trial comparing VenaSeal[™] cyanoacrylate occlusion plus normal treatment with normal treatment alone in patients with ipsilateral venous leg ulceration and Duplex-detected lower limb vein incompetence.

Normal treatment in both groups is defined as nurse-led dressing of the ulcer using a low adherence dressing and four-layer compression bandaging. Patients randomized to the treatment arm will also undergo cyanoacrylate occlusion using the VenaSealTM system.

The study will begin with 5 patients undergoing VenaSeal treatment as 'roll in' cases. Following these patients' treatment, the study proper will begin. Randomisation software will be used to allocate patients who fulfil inclusion / exclusion criteria to either the treatment arm or the non-treatment arm. This will be done to a 1:1 ratio, with 25 patients in each arm.

Patients will be followed up via face-to-face consultations at 3, 6 and 12 months post-randomisation.

INCLUSION CRITERIA

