
- a) Cost and frequency of visits to wound care and outpatient clinic.
- b) District nurse visit costs
- c) Inpatient treatment costs

d) Costs of complications of the treatment, or of non-healing ulcers (for example, acute or chronic infections).

STATISTICAL METHOD / RATIONALE

The main aim of the pilot study is to inform a larger, more definitive study by assessing feasibility and describing the main outcomes for the patients in the study. As such, the main analysis will be summary statistics. Simple statistical tests will be used to compare the groups, though these analyses are exploratory and non-definitive since the study is a pilot and has a limited sample size.

Time from intervention to healing, one part of the primary outcome, will be described in the two randomised groups using medians, interquartile ranges and ranges (minimum to maximum), assuming the data will be non-normally distributed. The other component of the primary outcome, the mean % ulcer healed per week², will be calculated for each patient

² The mean % ulcer healed per week will be calculated up to the point where the ulcer has fully healed (the primary endpoint). No further measurements will be calculated after this point.

and summarised in the two groups using means, standard deviations and ranges, assuming the data will be normally distributed.

The secondary endpoints will also be assessed using descriptive statistics. The composite VEINES-QOL/Sym score will be calculated using the intrinsic scoring method detailed in the Bland et al. validation paper.⁷ The composite summary scores will be described at each point they are assessed using means, standard deviations and ranges.

The rate of venous recanalization in each group will be summarised using frequencies and percentages. The number of adverse events and percentage in each group will be presented.

The statistical analyses used to compare the groups will be independent samples t-tests, Mann-Whitney U tests, and chi-squared tests.

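### The exploratory comparison of the arms is specified as significance tests only; a between-arm difference with a confidence interval should be added (minor, cheap improvement)

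*Protocol*

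**What the plan says.** All of this stands in the protocol's Statistical Method / Rationale section, except the sample size, which is under Study Design.

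- Purpose: "The main aim of the pilot study is to inform a larger, more definitive study by assessing feasibility and describing the main outcomes".
- Main analysis: "As such, the main analysis will be summary statistics".
- Status of the tests: "these analyses are exploratory and non-definitive since the study is a pilot and has a limited sample size".
- Arm-by-arm description: healing time by median, interquartile range and range. The mean percentage of ulcer healed per week is calculated for each patient and "summarised in the two groups using means, standard deviations and ranges, assuming the data will be normally distributed". The VEINES composite is described by mean, SD and range at each assessment. For recanalization, "The rate of venous recanalization in each group will be summarised using frequencies and percentages"; adverse events are given as numbers and percentages.
- Comparison of the arms: "The statistical analyses used to compare the groups will be independent samples t-tests, Mann-Whitney U tests, and chi-squared tests".
- Size: "This will be done to a 1:1 ratio, with 25 patients in each arm".

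Under Primary Objectives, the first question asks whether adding VenaSeal speeds healing and shortens the time to it, which is a question about a difference between arms. The protocol names no difference in means or medians, no risk difference, no hazard ratio and no confidence interval. It also states no significance level, power, effect size or target precision.

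**The concern.** A pilot that is to inform a larger trial serves it best by showing which treatment effects remain compatible with its data. A test result does not show that. At this sample size a non-significant p-value is likely even when a moderate effect exists, and a reader who is given two arm summaries and a p-value may take it as evidence of no effect. The exploratory label asks for caution but does not say how wide the uncertainty is.

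Most of the loss can be repaired afterwards from the reported summaries. For healing time it cannot. That is one of the two components of the primary outcome, so the plan as written would leave the size and uncertainty of the treatment effect on it unreported and unrecoverable from the report.

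**Working it through.** **Inputs.** From the protocol: 25 patients per arm, 1:1. Assumed, because the protocol gives none of them: two-sided 5% level, 95% intervals, no dropout, equal SD in both arms, and the effect sizes and event rates below. The 25 per arm cannot be reproduced, since no basis for it is stated.

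**1. Precision of a difference in means.** Half-width = t(0.975, 48 df) × √(2/25) = 2.011 × 0.2828 = 0.569, or about 0.57 SD. The same figure is the smallest observed difference that reaches p < 0.05.

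**2. Power of the t-test.** Noncentral t with 48 df and noncentrality d × √12.5:

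| True difference (SD) | Noncentrality | Power |
|---|---|---|
| 0.3 | 1.06 | 18% |
| 0.5 | 1.77 | 41% |
| 0.8 | 2.83 | 79% |

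Power of 80% needs a true difference of about 0.81 SD.

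**3. What the interval adds.** Suppose the observed difference is 0.3 SD. Then t = 0.3 × √12.5 = 1.06 and p = 0.29. The 95% interval is 0.30 ± 0.57, that is −0.27 to 0.87 SD. The p-value reads as a null result. The interval shows that the data are compatible with a modest disadvantage and with a large benefit.

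**4. Binary outcomes.** With assumed adverse-event percentages of 10% and 20%, the simple half-width is 1.96 × √(0.1 × 0.9/25 + 0.2 × 0.8/25) = 0.196, or about 20 percentage points. For recanalization in the VenaSeal arm, 2 of 25 is 8%, the upper bound that the Background section gives for first-year recanalization in non-comparative studies. The exact 95% interval for 2 of 25 is 1.0% to 26.0%. The planned frequency and percentage would not show this width.

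**5. Healing time.** With equal allocation, the approximate 95% interval for a hazard ratio is the estimate divided and multiplied by exp(1.96 × 2/√events). The factor is 1.74 if all 50 ulcers heal, 1.86 with 40 healed and 2.05 with 30 healed (numbers healed assumed).

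**6. What a reader could rebuild from the planned output.**

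| Outcome | Planned summary per arm | Interval for the difference recoverable? |
|---|---|---|
| % healed per week, VEINES score | Mean, SD, range | Yes, from means, SDs and n |
| Recanalization, adverse events | Counts and percentages | Yes, if they count patients |
| Healing time | Median, interquartile range, range | No |

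**The case against.** The strongest reply is that the protocol already treats the tests as it should. Summary statistics are the main analysis, and the tests are declared exploratory and non-definitive. No threshold or decision is tied to a p-value. That stands, and it is why the point is minor. A reader might infer that the plan delivers mainly p-values; the text does not support this. The planned SDs and percentages are useful for planning, and the tests work on patient-level values. With 48 degrees of freedom, the 95% interval for a pooled SD runs from 0.83 to 1.25 times its estimate.

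A second reply is that effect measures and intervals commonly belong in a statistical analysis plan, which may exist. This stands in part: nothing in the sentence forbids reporting them, and a t-test is itself built on the mean difference and its standard error. But the protocol does not leave the method open. It states how the arms will be compared, and every method in the list is a test.

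A third reply is that intervals can be derived from the published summaries. That is right for means and counts, and wrong for healing time.

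A reader might also infer that a significant pilot result must exaggerate the effect, and that the larger trial would be sized on it. Neither follows. Significance needs an observed difference of about 0.57 SD, so if the true difference were 0.8 SD a significant estimate could lie below it. The protocol nowhere says that the next trial will be sized on the observed difference.

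**Conclusion.** The point holds as a cheap improvement of minor severity. The only methods named for the exploratory comparison are three significance tests, without a between-arm difference or an interval, in a study that asks a comparative question and is meant to inform a larger one. With 25 per arm, the unreported uncertainty is about ±0.57 SD for a mean, and power is 18% at 0.3 SD and 41% at 0.5 SD. These figures assume a two-sided 5% level, complete data and those effect sizes; dropout would widen the intervals and lower the power. The one real loss of information is for healing time.

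The documents do not support a stronger verdict that the analysis is invalid or the pilot uninformative. The power figures show how little a p-value alone conveys here. They are not a criticism of the sample size, because the protocol claims no confirmatory test.

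**What to change.** In the Statistical Method / Rationale section, replace the sentence that lists the tests with wording such as:

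> Exploratory comparisons will report the between-arm difference with its 95% confidence interval: the difference in means for % ulcer healed per week and for quality-of-life scores; a time-to-event effect measure for healing time, with ulcers unhealed at last follow-up censored; and the risk difference with a Newcombe interval for binary outcomes. The recanalization percentage in the VenaSeal arm will be given with an exact 95% confidence interval. P-values, if given, are secondary.

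Healing time needs a time-to-event measure because a plain shift in location, such as a Hodges-Lehmann estimate, does not handle ulcers still unhealed at 12 months.

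The cost is a few sentences and a little more analysis work on the same data; trial conduct does not change. The one downside is that the results will visibly look less certain.
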